5.2 Study Outcome Measures

5.2.1 Primary Outcome Measure

The primary outcome is clinically diagnosed diarrhea anytime within 14 days of enrollment. Diarrhea is clinically defined as three or more loose stools per day for two consecutive days. This will be a dichotomous (yes or no) outcome of diarrhea during the 14-day period.

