10.1 ADVERSE EVENTS

An adverse event (AE) refers to any untoward medical occurrence in a clinical investigation subject administered an investigational product and which does not necessarily have a causal relationship with the treatment. An AE can therefore be any unfavorable and unintended sign, symptom, or disease temporally associated with the use of the investigational product, whether or not considered related to the product. This includes events not present at the start of the study or worsening during the course of the study even if present at the study start. An AE can be reported anytime after study enrollment; a participant is considered enrolled once the informed consent form is signed by the parent/caregiver.

Details of all solicited and unsolicited adverse events reported by parents/caregivers or observed by research personnel must be recorded in the adverse event report forms. Parents/caregivers will be provided with cards, which will list the most likely possible adverse events (see **Table 9**), where they can record solicited and other unsolicited events not already listed. All adverse events observed must be recorded separately and all must be reported to the IRB on IRB AE forms. All AEs regardless of severity level will be evaluated by full DSMB during scheduled meetings. The severity of adverse events will be recorded as follows:

- Mild (Grade 1): no or minimal interference with the subject's daily activity with intervention not indicated
- Moderate (Grade 2): some interference with the subject's daily activity but with intervention indicated
- Severe (Grade 3): prevents subject's daily activity and requires medical intervention
- Potentially Life Threatening (Grade 4): ER visit or hospitalization, with intervention indicated to prevent permanent impairment, persistent disability, or death
- Fatal (Grade 5): death

Based on the safety record of the yogurt, we anticipate that the following are the most likely AEs:

 Gl distress including: bloating, flatulence, nausea, emesis, anorexia, constipation and diarrhea • Allergic reactions including: anaphylaxis, hives, shortness of breath, rash, wheezing, and other reactions that the parent/caregiver or doctor believes may be related to food.

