11.3 STATISTICAL ANALYSIS PLAN FOR PRIMARY AND SECONDARY OUTCOMES

Initially, descriptive statistics (means, medians, frequency distributions, standard deviations, boxplots, etc.) for all characteristics will be examined for each group. Either parametric or nonparametric statistical (depending on results from the descriptive statistics) tests will be used for comparing results of the randomization. Because recruitment will take place over a long period (projected 3.5 years), descriptive statistics will further be examined in 4-6 month intervals (depending on the frequency of enrollments). This is to check that there are no patterns or differences in the subject characteristics over the enrollment time period. As the trial progresses, these characteristics will be continuously monitored and compared, so at that moment if there are differences in the distributions over time, the study team and the Data Safety Monitoring Board can convene to discuss. Additionally potential covariates, such as, age at entry, sex, weight of subject, time of year, etc., will also be statistically examined using univariate statistical tests.

For testing the primary objective (Aim 1), i.e., comparing the rates of AAD between the BB-12 and control groups, Fisher's Exact Probability test will be used. The relative risk of AAD for BB-

12 versus control and the 95% confidence interval will be calculated to display magnitude of the relationship. If the rates of AAD need to be adjusted for covariates, then multiple logistic regression models will be employed for predicting the adjusted rates of AAD. Covariates will be examined for multi-collinearity so as not to saturate the multiple logistic regression models constructed. With this large number of subjects enrolled, it is not expected that the number of AAD cases will be small enough to warrant further statistical methods. However, if the number of AAD cases is very small then exact statistical testing methods will be exclusively used for making the comparisons and performing any pertinent subgroup analyses. The Pediatric Quality of Life Inventory™ (PedsQL™) has a validated and easy scoring system.[104, 105]

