For Aim 2, numerous exploratory techniques (i.e., all descriptive statistics previously mentioned) will be performed to verify that the probiotic is safe and well tolerated. Additionally, the AEs will be collected and studied over time of enrollment. The rates of AEs will be estimated, 95% confidence interval be constructed for describing precision and statistically compared between groups. This will be accomplished using parametric or nonparametric tests. Further, in order to accurately identify patient populations or subgroups that can benefit from the BB-12 probiotic, decision tree models will be examined. Using decision trees, we may be able to identify groups of subjects that have no AEs versus those with an AE. Similarly, cluster analyses may also be employed to identify potential pockets of subjects that share similar characteristics but differ with respect to AEs. This is related to an area known as "unsupervised" modeling in data mining, but is appropriate in this Phase II trial for finding subgroups of subjects that have plausible similarities and also differences.

Statistical analysis will be performed using the intention to treat principle; all subjects enrolled and randomized will be accounted for in the final analysis in their randomized group. One interim analysis will be performed when approximately 50% of the subjects have been recruited. While the alpha for stopping the trial will be set at 0.01, it is unlikely that we would want to stop this trial at that point even if significance is achieved, but the Data Safety Monitoring Board, PI and NIH representative will make that final decision. For Aim 1, the level of significance for the primary objective will be tested at alpha = 0.029 to account for the one interim analysis.

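### Decision trees whose only stated target is AE versus no AE are said to identify who benefits from BB-12; the plan states no between-arm AAD contrast that could show this

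*Combined protocol and SAP*

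**What the plan says.** The trees appear in the Aim 2 (safety) paragraph of section 11.3, which opens: "For Aim 2, numerous exploratory techniques (i.e., all descriptive statistics previously mentioned) will be performed to verify that the probiotic is safe and well tolerated". The same paragraph gives their purpose: "in order to accurately identify patient populations or subgroups that can benefit from the BB-12 probiotic, decision tree models will be examined". The next sentence gives the only target: "Using decision trees, we may be able to identify groups of subjects that have no AEs versus those with an AE". The companion method has the same target: "cluster analyses may also be employed to identify potential pockets of subjects that share similar characteristics but differ with respect to AEs". Tree inputs are not listed, so randomized arm is neither named nor excluded.

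Benefit is set out elsewhere. Section 5.2.1: "The primary outcome is clinically diagnosed diarrhea anytime within 14 days of enrollment". Hypothesis 1 in section 11.1 expects less diarrhea on BB-12 than on control, and section 11.3 tests this for the whole sample: "comparing the rates of AAD between the BB-12 and control groups, Fisher's Exact Probability test will be used". For subgroups, the Aim 1 text mentions pertinent subgroup analyses in passing, with no list and no interaction method.

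Section 10.1 counts AEs "whether or not considered related to the product". Its Table 9 lists diarrhea, with the primary-outcome definition, beside fever, rash, vomiting, cough, nasal congestion and others. Table 8 runs AE reporting to Day 180.

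**The concern.** The stated purpose and the stated target answer different questions. A subgroup benefits if its AAD rate is lower on BB-12 than on control, which needs AAD as the outcome and a comparison of arms within the subgroup. A tree on AE yes/no sorts children by how likely they are to have any event. Calling the work exploratory lowers the standard of proof. It does not change the quantity estimated, and the claim of accuracy in the purpose clause goes beyond an exploratory aim.

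What is at stake is a secondary statement about which children the product helps. If AE-based groups were described in the terms of the purpose clause, that statement would lack the comparison it needs.

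**Working it through.** The plan gives no figure for this analysis, so there is none to reproduce. The check is of target against purpose, with illustrations that use assumed AE rates.

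**1. How much of AE status is diarrhea?** The sponsor's earlier studies (section 4.1.9) give a rough idea.
- Phase I pediatric study, days 0-10 (Table 2): diarrhea 2 + 2 = 4 of 96 events. Runny nose 18, cough 15 and nasal congestion 10 make 43 of 96.
- Phase I adult study on antibiotics (Table 1): diarrhea 2 + 2 = 4 of 98 + 67 = 165 events.

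These are event counts in other populations, with loose stool listed separately. They suggest that AE status would mostly reflect events other than AAD.

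**2. Can an AE split reveal benefit?** Simulation with 300 children randomized 1:1, 4,000 replicates and one binary covariate X at 50%. AE status was drawn independently of AAD. A split counts as found when X separates AE from no AE at two-sided 0.05.

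| Assumed truth | X separates AE from no AE | AAD difference, control minus BB-12, in the two levels of X |
|---|---|---|
| AE 50% vs 20% by X; AAD 0.22 vs 0.08 everywhere | about 100% of trials | 0.14 and 0.14 |
| AE 35% everywhere; AAD 0.22 vs 0.02 if X=1, 0.22 vs 0.22 if X=0 | 4.8% of trials (chance rate) | 0.20 and 0.00 |

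The first row finds groups that do not differ in benefit. The second misses the group that does.

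**3. The second row again, with diarrhea counted as an AE.** Let q be the rate of any other AE, independent of AAD. With the arms pooled, AAD is (0.22 + 0.02)/2 = 0.12 if X=1 and 0.22 if X=0. AE rate = 1 − (1 − q)(1 − AAD rate). At q = 0.35:
- X=1: 1 − 0.65 × 0.88 = 0.428; X=0: 1 − 0.65 × 0.78 = 0.493; difference 0.065.
- The mean rate is 0.4605, so SE = sqrt(2 × 0.4605 × 0.5395/150) = 0.0576 and z = 1.13.
- Chance of finding X = Φ(1.13 − 1.96) = about 0.20. The same steps give about 0.31 at q = 0.20 and 0.08 at q = 0.80.

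Some signal therefore gets through, but it cannot be read as benefit. A group with AAD of 0.12 in both arms, and so no benefit, has the same pooled AE rate of 0.428.

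**4. If arm were a tree input.** The arm difference in AE rate for X=1 would be (1 − q) × 0.20: 0.13 at q = 0.35 and 0.04 at q = 0.80. It would also be mixed with any effect of BB-12 on the other events.

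**5. What a direct analysis could show.** Section 11.2 gives 0.22 vs 0.08 with 150 per group. Two equal subgroups give 75 per cell; alpha is 0.05 two-sided and the interaction is 0.14.
- SE taken from identical rates in both subgroups: main-effect SE = sqrt(0.22 × 0.78/150 + 0.08 × 0.92/150) = 0.0404; interaction SE = 2 × 0.0404 = 0.081; 0.14/0.081 = 1.73; power = Φ(1.73 − 1.96) = 0.41.
- SE taken from an effect in one subgroup only (0.22 vs 0.08 against 0.22 vs 0.22): SE = sqrt(3 × 0.22 × 0.78/75 + 0.08 × 0.92/75) = 0.089; 0.14/0.0886 = 1.58; power = Φ(1.58 − 1.96) = 0.35.

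**The case against.** The case for leaving the text alone has four parts.

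- **Diarrhea is itself a listed AE.** This is true, and it rules out a tempting stronger reading: that the trees contain nothing of the efficacy outcome and carry no information on who benefits. The event is present but diluted, as step 3 of the working shows.
- **Arm is not excluded.** Also true. A reader might infer that no arm comparison would be made, but the text is only silent, and the same paragraph compares AE rates between groups. Adding arm would turn the tree towards differential tolerability, which is still not prevention of AAD.
- **The work is hedged and exploratory, in a safety paragraph of a Phase II trial.** No stopping rule or confirmatory test depends on it, and the text does not commit the trial to publishing AE-based groups as responders. Benefit is not defined in that paragraph, so equating it with less AAD is a reading, though it is the one that section 5.2.1, Hypothesis 1 and the Aim 1 analysis support.
- **Responder questions arise elsewhere.** Sections 11.4.3 and 11.4.5 consider enterotypes in relation to diarrhea and to response to BB-12. That work concerns microbiota, and it supplies no interaction analysis of AAD on clinical covariates.

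These points limit the size of the problem. None makes AE status a measure of benefit.

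**Conclusion.** The point holds at modest severity. As written, the tree and cluster analyses can describe susceptibility to AEs; they cannot support a conclusion about which children benefit from BB-12. This rests on taking benefit to mean less AAD within 14 days on BB-12 than on control, and on AE status being the trees' only stated target. The simulation and the values of q are illustrations with assumed rates, not forecasts.

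A reader might go further and conclude that the efficacy analysis is compromised. The documents do not support that: the Fisher test and its significance level do not depend on the trees. Nor do the powers of 0.35 to 0.41 measure harm from the present text. They describe the replacement analysis and show that accurate identification would be optimistic even with the right outcome.

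**What to change.** In section 11.3, restate the purpose of the trees and clusters as an exploratory description of AE risk, say whether randomized arm is an input, and delete the clause claiming accurate identification of subgroups that can benefit.

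For benefit, add an analysis with AAD within 14 days as the outcome and a short, pre-named list of treatment-by-covariate interactions on covariates already collected, such as age, sex and antibiotic prescribed. Report the arm difference within each subgroup and the interaction, with confidence intervals, labelled hypothesis-generating.

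The cost is SAP wording and a few extra models on data already collected. The downside is imprecision: a null interaction would not show that the effect is uniform, and the report should say so.

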II. Safety of BB-12 Supplemented Strawberry Yogurt For Healthy Children: The primary objective of our Phase 1 pediatric study was to assess the safety of strawberry flavored yogurt supplemented with Bifidobacterium animalis subsp. lactis strain BB-12 when consumed daily for 10 consecutive days by generally healthy children. The secondary objective was to assess the ability of BB-12 to survive gastric transit. The participants in the study were healthy individuals between the ages of 1-5 years. Participants were recruited through CAPRICORN. Twenty-nine participants received the BB-12 yogurt and 31 participants received the control yogurt. All reported adverse events were tabulated by type and treatment group (Table 2). Three serious adverse events were reported (details in Table 2). No participant deaths were reported and no participants withdrew from the study due to adverse events.

Both studies, Safety of BB-12 Supplemented Strawberry Yogurt For Healthy Adults on Antibiotics and Safety of BB-12 Supplemented Strawberry Yogurt For Healthy Children were conducted under the same IND.

Table 2. Phase I Pediatric Study Adverse Events

	Days 0-10			Days 11-180		
	(During Intervention)			(Post-Intervention)		
Event	Control	BB-12	Total	Control	BB-12	Total
Allergies (e.g. seasonal)	1	2	3	1	3	4
Broken finger					1	1
Bronchiolitis					1	1
Cold	2		2	2	1	3
Constipation		3	3	2	1	3
Cough	5	10	15	1	5	6
Croup					1	1
Cut finger				1		1
Diarrhea	2	2	4	2	5	7
Ear aches					1	1
Ear infection				2	1	3
Fever		2	2	2	3	5
Flatulence	2	2	4	1	1	2
Headache				1		1
Hives		1	1			
Irritability	4	1	5	3	5	8
Laceration				1		1
Lack of/decreased appetite	2	2	4	3	1	4
Lethargy	1	5	6			
Loose stool	2	6	8	3	3	6
Lump on back of head				1		1
Nasal congestion	4	6	10		2	2
Pain	2	1	3	2		2
Physical injury				1		1
Pink eye					1	1
Pneumonia					1	1
Rash		2	2	1	2	3
Runny nose	6	12	18	6	9	15
Skin infection				1		1
Sore foot					1	1
Sore throat	1	2	3			
Strep throat					1	1
Umbilical hernia	1		1			
Vomiting		2	2	1	2	3
Total	35	61	96	38	52	90
Serious adverse events ^a		1	1		2	2

^a Serious adverse events included: 1) grade 4/potentially life-threatening fever reported on day 2, 2) grade 4/potentially life-threatening bronchiolitis reported at day 180 and 3) grade 4/potentially life-threatening pneumonia reported at day 180. All serious adverse events were unrelated to the interventions and resolved.

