4.3 Potential Risks and Benefits

4.3.1 Potential Risks

Yogurt: Potential risks and side effects related to the probiotic cultured yogurt include: allergic reaction to drink ingredients, most likely strawberry, or digestive problems such as stomachaches or loose, watery bowels due to lactose intolerance.

There may also be side effects, other than those listed above that we cannot predict. Many side effects may go away shortly after the yogurt consumption is stopped, but in some cases side effects can be serious, long lasting or permanent.

Stool Collection: There is no known risk to stool collection. However, there may be some discomfort with collecting stool samples.

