9.3.1 Telephone Follow Up Script

In general, the Day 7, 11, 14, and 180 (±2 days) follow up will be administered over the phone, but may be completed in person. These phone visits are when the primary data will be collected. It is imperative that all visits be completed on a timely and regular fashion.

- 1) *Drink Number:* Make sure the parent/caregiver has the correct drink number as you are completing the Follow-Up Form.
 - a) Ask the parent/caregiver the number on the drink bottles and this should be confirmed with the computer program provided by the data manager.
 - b) If this number is not consistent, the parent/caregiver should be alerted not to give their child any more drinks and the project coordinator should be immediately alerted after completing this week's Follow-Up Form
- 2) Daily Assessment Diary: Ask the parent/caregiver to collect the Daily Assessment Diary for the phone conversation. A lot of the information that will be collected on the Follow-Up Form has been collected by the parent/caregiver on their Daily Assessment Diary. If they have not been using the Daily Assessment Diary, please positively stress the importance of the Daily Assessment Diary.
- 3) Explain to parent/caregiver that we are supposed to fill out this Follow-Up Form today and it should take about 5 minutes.

4) Administer Follow-Up Form.

- When entering sick days, missing school or daycare, etc., this should be generally whole
 integers. However, it is possible that a child missed only 2 hours to go to the doctor. All
 numbers under 4 hours should be counted at 0.5 days, and all those above rounded up
 to next integer.
- The parent/caregiver needs to decide if any activities were missed due to an illness. This is for all illnesses, even those that we are not collecting data about.
- For some questions the RA may say, "Did your child visit a doctor?" A doctor is defined as any medical personnel in this study. Therefore, the parent/caregiver may say, "Never, but s/he saw a nurse practitioner." Please count this the same as seeing the doctor.
- Satisfaction Questions: Please provide the parent/caregiver with the numbers s/he stated the prior time for a comparison.
- Compliance: Please let the parent/caregiver know that we would like them to give their child the drink every day, but regardless, we appreciate their participation.
- Adverse Events: If the parent/caregiver believes any AE occurred, it is imperative that

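### The safety comparison (Aim 2) has no exposure-based analysis set and no adverse-event periods, so off-product events mix with on-product ones; pooling can mask an acute effect, and an on-product window alone can miss a later one.

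*Combined protocol and SAP*

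**What the plan says.** Section 11.3 describes the Aim 1 and Aim 2 analyses and then sets a single analysis rule, intention to treat, with no exception for safety. It spells the rule out by adding that "all subjects enrolled and randomized will be accounted for in the final analysis in their randomized group". For Aim 2 it says: "The rates of AEs will be estimated, 95% confidence interval be constructed for describing precision and statistically compared between groups". No denominator, minimum exposure or period is attached. The only time reference is that "the AEs will be collected and studied over time of enrollment".

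Section 10.1 opens by defining an AE as an event in a subject who has been given the investigational product, temporally associated with its use. The same paragraph then says: "An AE can be reported anytime after study enrollment; a participant is considered enrolled once the informed consent form is signed by the parent/caregiver".

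Under Section 9.2 the baseline stool comes before the first serving, and after a virtual enrollment the yogurt is delivered once signatures are in. Section 9.3.1 foresees a bottle whose number does not match: "If this number is not consistent, the parent/caregiver should be alerted not to give their child any more drinks". It gives no rule for analyzing that child's events. The protocol summary gives 7-10 days on product, while the AE row of Table 8 runs to Day 180. In Section 4.1.9, Table 2 (Phase 1 pediatric study) reports AEs separately for Days 0-10, during intervention, and Days 11-180, after it.

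**The concern.** Intention to treat is a sound default for efficacy. For safety the question is what happens to children who take the product, and when. As written, three kinds of event unrelated to the assigned product can enter the arm comparison: those between consent and first serving, those in children who drank nothing, and those in children who drank the other product. On-product events are also merged with events from a follow-up many times longer than the course.

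Some of the harms named are acute. Besides allergic reaction, Section 4.3.1 lists "digestive problems such as stomachaches or loose, watery bowels due to lactose intolerance". A short-lived excess of that kind is easy to lose in a total that runs to Day 180. Safety is a stated secondary objective, and the plan intends Aim 2 to verify that the product is safe and well tolerated, so the comparison should show both when events happened and what the child had actually taken.

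**Working it through.** **1. The plan's own figures.** No power or precision figure is given for Aim 2. The Aim 1 power in Section 11.2 (150 per group, 0.22 v 0.08, two-sided 0.05, stated 0.92) reproduces at 0.928 by the normal formula and 0.914 by exact Fisher calculation; this point does not affect it. The rows of Table 2 add up to the printed totals of 35, 61, 38 and 52.

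**2. Events per child in Table 2.** Denominators are 29 (BB-12) and 31 (control), from Section 4.1.9. Ratio = (BB-12 events / 29) / (control events / 31).

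| Event | Period | BB-12 | Control | Ratio |
|---|---|---|---|---|
| Loose stool | Days 0-10 | 6 | 2 | 0.207 / 0.065 = 3.21 |
| Loose stool | Days 11-180 | 3 | 3 | 0.103 / 0.097 = 1.07 |
| Loose stool | Pooled | 9 | 5 | 0.310 / 0.161 = 1.92 |
| Diarrhea | Days 0-10 | 2 | 2 | 0.069 / 0.065 = 1.07 |
| Diarrhea | Days 11-180 | 5 | 2 | 0.172 / 0.065 = 2.67 |
| Diarrhea | Pooled | 7 | 4 | 0.241 / 0.129 = 1.87 |
| All AEs | Days 0-10 | 61 | 35 | 2.10 / 1.13 = 1.86 |
| All AEs | Days 11-180 | 52 | 38 | 1.79 / 1.23 = 1.46 |
| All AEs | Pooled | 113 | 73 | 3.90 / 2.35 = 1.65 |

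Of all 186 events, 90 (48%) fell after the product period. The all-AE excess per child is 2.10 - 1.13 = 0.97 on product and 3.90 - 2.35 = 1.54 pooled. So the ratio shrinks on pooling while the difference grows.

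**3. What this could mean with 150 v 150.** Assumption: each Table 2 event is treated as one child. Exact Fisher power, two-sided 0.05:

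- Loose stools at the Table 2 rates: 0.946 on product (6.5% v 20.7%), 0.838 pooled (16.1% v 31.0%).
- Smaller assumed acute excess: 0.702 on product (6.5% v 16%), 0.469 once an assumed 10% later background is added to each arm (16.5% v 26%).
- Diarrhea at the Table 2 rates: 0.03 on product (6.5% v 6.9%), 0.66 pooled (12.9% v 24.1%).

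The first two lines show pooling hiding an acute effect. The third shows an on-product window hiding a later one.

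**4. Unexposed and wrong-product children.** Their shares are not given. Assume a true risk of 10% v 20% and no background events. Normal-formula power is 0.68 if every child takes the assigned product, and 0.61 with 5% never dosed and 2% on the other product. For an event never seen, the one-sided 95% upper limit is 1 - 0.05^(1/n): 2.0% for n = 150, 2.1% for n = 143 (about 5% undosed) and 2.2% for n = 135 (10% undosed). Both effects are small.

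**The case against.** A reader might infer that the plan biases the safety comparison toward no difference, and that the on-product window should therefore be primary. The documents do not support that. In Table 2 the all-AE excess continues after the product stops, and treating the counts as Poisson the contrast strengthens on pooling (z about 2.9 to 3.4). Diarrhea, which Section 10.1 names among the likeliest AEs, shows no on-product difference but 7 v 4 overall. Two of the three serious events, all in the BB-12 arm and all judged unrelated, were reported at Day 180. Ranking the later period second could hide such patterns.

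Other points also stand in part:

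- Read literally, the first AE definition in Section 10.1 excludes pre-dose and never-dosed events. It conflicts with the reporting rule in the same paragraph rather than settling the matter.
- The earlier daycare trials reported compliance above 92% (Section 8.1.6), and Table 8 starts the yogurt in the Day 0/1 column, so undosed children and pre-dose events are probably few.
- Section 8.4.2 lists six drink numbers for two arms, so a mismatched number need not mean the other product.
- The diary ends on Day 14 and the next follow-up call is at Day 180, where parents are asked about events they link to the yogurt. Late background may be recorded less fully than in Phase 1.
- The time-of-enrollment wording may mean calendar time or time since a child's own enrollment. Neither is time since first serving.
- Aim 2 is exploratory, and the plan does not forbid additional tables.

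None of this supplies a safety set or a period, and parental attribution is no substitute for either.

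**Conclusion.** The gap is real and worth closing before analysis. The plan sets no exposure requirement and no AE period for Aim 2, and Section 10.1 contradicts itself on when an AE can first arise. The consequence that matters most is the mixing of on-product and later events, which can mislead in either direction: loose-stool ratio 3.2 on product against 1.9 pooled, but diarrhea 2 v 2 on product and 5 v 2 afterward. The direction of any bias in this trial is not established.

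Table 2 counts events, possibly several per child, in 60 children. It shows direction only and supports no valid interval. The power figures rest on one event per child and on assumed background rates. The effect of never-dosed and wrong-product children cannot be sized from the documents and is probably small.

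**What to change.** 1. In Section 11.3, limit the intention-to-treat sentence to efficacy.
2. For Aim 2, define a safety set of children who took at least one serving, grouped by product actually received.
3. Count events that start or worsen after the first serving, and list earlier ones separately by arm.
4. Show the arm comparison for the on-product period, for the later period to Day 180 and for the total, with neither period demoted.
5. Keep the randomized-arm table as a sensitivity analysis.
6. Reconcile the two AE statements in Section 10.1. Reconcile also the two statements in Section 8.2, a 7-10-day supply and ten consecutive days of drinking, so that the on-product period is defined. Which is intended is for the sponsor to say.

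No new procedures should be needed. Time of first serving (Section 9.3), daily intake (Section 8.5), drink number (Section 9.3.1), and the AE forms and daily diary already exist; the sponsor should confirm that the AE form gives an onset date. The cost is SAP wording and one more set of tables. The downside is that a few children may leave the safety denominator or change group within it.

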11.2 SAMPLE SIZE CONSIDERATIONS

Sample Size Calculation for the Primary Outcome: This study is a double blinded, randomized Phase II trial where subjects will be randomly assigned (1:1) to either a probiotic (BB-12) yogurt group or to a control yogurt group. The primary outcome is dichotomous, clinically diagnosed diarrhea or no diarrhea, with the rate of AAD in the general population estimated to be 20-35%. Preliminary results from the Cochrane review showed the incidence of AAD in a high dose probiotic group to be 8% versus 22% in a control group.[108] Using the Cochrane estimates, a total sample of 300 subject (150 per group) would provide a power of 0.92 for detecting a difference of 0.14 (0.22 control - 0.08 probiotic) at alpha = 0.05, 2-tailed. To allow for one interim analysis (at approximately 50% recruitment), and then adjusting the final p-value to 0.029, the power would still be 90% for detecting the difference of 0.14 in the rates of AAD. If the difference in the final rates is smaller than 0.14, such as 0.12, the resulting power would still be sufficiently large (80%) and power would be equal to 74% if the final difference in rates were equal to 0.10. While the hypothesis is one-sided (see Aim 1; we expect children receiving probiotic intervention will demonstrate less AAD than those receiving the control product), we still used a two-tailed alternative for estimating the sample size in order to be conservative. While multiple efforts are arranged to minimize loss of data, in order to obtain the primary outcome (diarrhea or no diarrhea), there still will be some participants lost to follow-up and the endpoint is unknown. Nonetheless, if the lost to follow-up rate is as high as 10% (then N=270, approximately 135 per group), power would still be 90% for detecting the difference of 0.14 and 80% for detecting a difference of 0.12.

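### The final alpha of 0.029 does not follow from a 0.01 interim look, and the N=270 power in section 11.2 does not hold at 0.029

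*Combined protocol and SAP*

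**What the plan says.** Section 11.3 plans one interim analysis when about half of the participants have been recruited. It gives a single interim level, "While the alpha for stopping the trial will be set at 0.01", and adds that "it is unlikely that we would want to stop this trial at that point even if significance is achieved". The Data Safety Monitoring Board, "PI and NIH representative will make that final decision". For the final analysis, "the level of significance for the primary objective will be tested at alpha = 0.029 to account for the one interim analysis". No boundary family or spending function is named, and the sidedness of 0.01 is not given. The primary test is Fisher's exact test. It is accompanied by a relative risk whose "95% confidence interval will be calculated to display magnitude of the relationship".

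Section 11.2 sizes the trial at 150 per group for 22% versus 8%, "at alpha = 0.05, 2-tailed", with stated power 0.92. After "adjusting the final p-value to 0.029, the power would still be 90% for detecting the difference of 0.14", it gives 80% for a difference of 0.12 and 74% for 0.10. With 10% loss (N=270, about 135 per group), it says "power would still be 90% for detecting the difference of 0.14 and 80% for detecting a difference of 0.12", without naming the alpha.

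**The concern.** The plan presents 0.029 as the price of the interim look. A look at 0.01 is cheap and should leave most of 0.05 for the final test. The value 0.029 is close to the level for two equal boundaries (0.0294 at each look), which would also test the interim at about 0.029. It looks like a final level from one design joined to an interim level from another.

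Three things are at stake:

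- Power is given up without a stated reason.
- A reader of section 11.2 believes that 90% power survives 10% loss to follow-up. One alpha cannot give 90% for the same rates at both N=300 and N=270.
- A 95% interval can exclude 1 while the primary test at 0.029 is not significant.

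**Working it through.** **Inputs.** From section 11.3: interim 0.01, final 0.029, one look at about 50%, Fisher's test, 95% interval. From section 11.2: overall alpha 0.05 two-sided, rates 0.22 and 0.08, 150 per group, or 135 after 10% loss. Assumptions: 0.01 is two-sided and information fraction t = 0.5, with alternatives shown.

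**1. Reproducing the stated power.** Power = Φ[(Δ − z·s0)/s1], where s0 = √(2p̄(1−p̄)/n) and s1 = √((p1(1−p1)+p2(1−p2))/n). For 0.22 versus 0.08:

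- n=150: s0 = 0.04123, s1 = 0.04043. At 0.05: (0.14 − 1.960×0.04123)/0.04043 = 1.464, power 92.8% (stated 0.92). At 0.029: (0.14 − 2.183×0.04123)/0.04043 = 1.236, power 89.2% (stated 90%). Both reproduce.
- n=135: s0 = 0.04346, s1 = 0.04262. At 0.05: 1.286, power 90.1%. At 0.029: 1.058, power 85.5%. The stated 90% reproduces only at 0.05. Exact Fisher power at 0.029 is 83.3%.

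**2. Alpha spent by the pair.** Overall alpha = 1 − P(|Z1| < c1, |Z2| < c2), with Z1 and Z2 bivariate normal and correlation √t = 0.707. For 0.01 and 0.029, c1 = 2.576 and c2 = 2.183.

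| Reading | Overall alpha with final 0.029 | Final level that uses 0.05 |
|---|---|---|
| 0.01 two-sided, crossing counts as rejection | 0.0348 | 0.0452 |
| 0.01 one-sided (0.02 two-sided) | 0.0422 | 0.0379 |
| Interim cannot support an efficacy claim | 0.029 | 0.05 |

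In the first row the final level is 0.0441 at t = 0.40 and 0.0464 at t = 0.60. A final 0.029 exhausts 0.05 only if the interim level is about 0.030.

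**3. Power at each final level** (formula of step 1, final test alone).

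| N | Rates | Stated | 0.05 | 0.0452 | 0.029 |
|---|---|---|---|---|---|
| 300 | 22% v 8% | 90% | 92.8% | 92.2% | 89.2% |
| 300 | 22% v 10% | 80% | 81.2% | 80.0% | 74.5% |
| 300 | 20% v 8% | 80% | 85.3% | 84.3% | 79.5% |
| 300 | 22% v 12% | 74% | 63.6% | 62.0% | 54.9% |
| 300 | 18% v 8% | 74% | 73.3% | 71.9% | 65.4% |
| 270 | 22% v 8% | 90% | 90.1% | 89.3% | 85.5% |
| 270 | 22% v 10% | 80% | 77.0% | 75.7% | 69.6% |
| 270 | 20% v 8% | 80% | 81.5% | 80.3% | 74.8% |

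Exact Fisher power at N=300, control 22%, counting both looks, final 0.029 against 0.045: 87.5% to 90.9% for a difference of 0.14, 71.0% to 76.8% for 0.12, and 50.4% to 57.3% for 0.10.

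**4. Interval against test.** Take 32/150 control and 18/150 BB-12 events. Fisher p = 0.043, not significant at 0.029. The relative risk is 18/32 = 0.5625, and the standard error of its log is √(1/18 + 1/32 − 2/150) = 0.271. The 95% upper limit is 0.5625·exp(1.960×0.271) = 0.96. The 97.1% upper limit is 0.5625·exp(2.183×0.271) = 1.02.

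The table gives the chance that the interval excludes 1 while Fisher's test is not significant, with 150 per group and control 22%:

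| True difference | 95% interval, test 0.029 | 97.1% interval, test 0.029 | 95.5% interval, test 0.045 |
|---|---|---|---|
| 0.14 | 6.0% | 2.2% | 1.7% |
| 0.12 | 10.7% | 3.6% | 3.3% |
| 0.10 | 13.6% | 4.2% | 4.3% |

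The part due to the mismatched level is therefore 3.8, 7.1 and 9.4 points. The rest comes from pairing Fisher's test with a Wald-type interval and will remain.

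**The case against.** A sponsor may choose a final level stricter than the maximum allowed. Type I error is protected, the plan says stopping is unlikely, and section 11.2 openly prices 0.029 at N=300. All of that stands, and it is why this is not a validity problem. But section 11.3 gives the interim analysis as the reason for 0.029, and a 0.01 look does not require it.

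A second defence is that 0.029 was meant as the significance level at both looks, with 0.01 only a stricter guide for stopping. That pair would spend 0.0494 and waste almost nothing. The plan does not say this: 0.01 is the only interim level it gives. If this was the intention, it has to be written down.

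Third, the interval is described as showing magnitude and does not decide the test. That is fair, and it makes the interval the least weighty of the three parts.

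Fourth, relaxing a prespecified threshold late in a trial invites criticism of its own. This stands too. Version 1.7 is dated July 2021, and the documents do not say whether the interim has taken place. The change is clean only if made before, or blind to, interim comparative data.

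None of these points rescues the N=270 power.

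**Conclusion.** The concern holds. On no stated reading is 0.029 the level that a 0.01 interim look requires. The pair spends about 0.035 two-sided (0.034 to 0.036 for information fractions of 0.6 to 0.4), 0.042 if 0.01 is one-sided, and 0.029 if the interim cannot support a claim. At N=300 with 22% in controls, the cost is about 3 points of power at a difference of 0.14, 5.5 at 0.12 and 7 at 0.10.

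The N=270 statement is wrong at the level the trial will use: about 86% instead of 90% for 0.14, and 70% to 75% instead of 80% for 0.12, depending on which rates give that difference. The stated 74% for 0.10 at N=300 likewise reproduces only at 0.05, with 18% versus 8%.

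These results rest on the normal approximation and an overall two-sided alpha of 0.05. The comparison of N=300 with N=270 needs no assumption about the boundary. This should be fixed, but it does not threaten the validity of the trial.

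**What to change.** 1. Keep the 0.01 interim level. State that it is two-sided and whether crossing it counts as rejection of the null hypothesis.
2. Derive the final level from the information fraction actually reached (about 0.045 at 50%). Do not fix 0.045 in advance, because a flat 0.045 gives an overall 0.0509 if the look falls at 40%.
3. Restate every power figure in section 11.2 at that level, naming the alpha and the pair of rates each time.
4. Report the relative-risk interval at the level of the final test.
5. Make the change before interim comparative data are seen, or have it made by people blind to them. Section 11.3 gives the PI a part in the stopping decision, so the PI may not be blind afterwards.

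If step 5 is no longer possible, keep 0.029, report a 97.1% interval, and restate the section 11.2 power at 0.029 (about 86% for 0.14 at N=270).

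The cost is one or two sentences in section 11.3, a rewritten power paragraph in section 11.2, and an amendment with the IRB approval that section 12.2 requires. No patients or new data are needed. Some spare conservatism is given up, but with Fisher's test at both looks the exact overall error at 0.01 and 0.045 is still only 0.034 to 0.036 (enumerated with 75 then 150 per group, null rates 0.15 and 0.22).
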